## **5. STUDY DESIGN**

### **5.1. STUDY OBJECTIVES**

The purpose of this study is to collate information from existing medical records for patients who received treatment with the Sensus Healthcare SRT-100™ for non-melanoma skin cancer (NMSC), both SCCs and BCCs, into a central registry database for the purpose of retrospective evaluation.

#### **5.1.1. Primary Objective**

The primary objective of this study is to evaluate the treatment outcomes of the retrospective data for long-term safety and efficacy of application of SRT-100™ for the treatment of NMSC (SCC and BCC), including long-term cure rates.

#### **5.1.2. Secondary Objectives**

The secondary objectives of this study are to evaluate the retrospective data for potential differences in treatment outcomes, including cure rates, based on lesion variables (such as tumor size and location, tumor type), patient characteristics (such as demographics), and treatment dosage/fractionation differences.

### **5.2. INVESTIGATIONAL PLAN**

#### **5.2.1. Collecting Sites**

There will be multiple participating sites located in the United States selected based upon having access to the required patient population medical records. There is no limit on the potential number of participating sites. Each identified and qualifying site that is willing to participate in the study will be included.

#### **5.2.2. Data Collection Methodology**

Patient data will be retrospectively collected from the medical records and other source documentation already existing in patient files at the participating sites.

### **5.2.3. Ethical Considerations**

This retrospective chart review qualifies for 'exempt' status under human subject regulations. Exempt studies are not subject to certain federal research requirements and do not require yearly recertification. The determination of 'exempt status' for this study is based on satisfaction of the following criteria: 1) The study involves the use of existing data, documents and records, with 'existing' defined as 'materials that are already in existence at the time of the study protocol development'; 2) The protocol specifies a date for data collection and review, that is, this study will only collect information that has been recorded in charts for patients who were treated for NMSC using the SRT-100™ prior to 01/01/2015; and 3) Information recorded will not contain any individual subject identifying information or data elements that may potentially link a patient to his or her data. That is, it will not be possible to figure out what data belongs to which patient once the data has been recorded in the central study database.

This retrospective study will meet Health Insurance Portability and Accountability Act (HIPAA) Privacy Requirements by satisfying the criteria for waiver of privacy authorization according to the following criteria: 1) There is an adequate plan to protect identifiers from improper use and disclosure; 2) There is an adequate plan to destroy any identifiers at the earliest opportunity; 3) Protected health information (PHI) will not be re-used or disclosed for another purpose; 4) The research could not practicably be conducted without the waiver of privacy authorization; and 5) The research could not practicably be conducted without the use of PHI.

## **5.3. STUDY DURATION, ENROLLMENT AND NUMBER OF SITES**

### **5.3.1. Duration of Study**

Applicable data elements to be reviewed in this study will be collected from patient records whose treatment of NMSC with the SRT-100™ occurred prior to 01/01/2015. All applicable and available data elements as specified in this study protocol will be recorded for each patient from the time of treatment forward to the most recent follow-up data entry date.

Therefore, the study duration of patient participation in this study according to the duration of the review of their medical records will vary individually based upon their initial SRT-100™ treatment date.

The entire study duration with respect to time from start of patient data identification and collation to completion of the final patient data entry will be dependent upon the time needed to identify all potential participating study sites and to collate all of the required available data from all qualifying patient records at each of those sites.

### **5.3.2. Total Number of Study Sites/Total Number of Subjects Projected**

There will be multiple participating study sites, all located in the United States. Each will be selected based upon having access to the required medical records of patients who were treated at their site for NMSC with the SRT-100™ prior to January 1, 2015, and for whom follow-up data is available. There is no limit on the potential number of participating sites. Each identified and qualifying site that is willing and able to participate in the study will be included.

Subject data will be retrospectively collected from the existing medical records in the identified qualifying patient files at the participating sites as those who were treated with the SRT-100™ for one or more NMSCs, who have follow-up data and who subsequently satisfy all of the inclusion criteria and none of the exclusion criteria for inclusion of their retrospective data in this study. There is no limit on the potential number of study subjects. The applicable retrospective data for each identified and qualifying subject at each participating study site will be included in the retrospective analysis.

## **5.4. STUDY POPULATION**

The study population comprises patients who were treated at one of the participating study sites with the SRT-100™ for one or more NMSCs, who have follow-up data and who satisfy each of the study inclusion criteria and none of the exclusion criteria.

### **5.4.1. Inclusion Criteria**

1. Male or female.
2. Treatment with SRT-100™.
3. Treatment date of December 31, 2015 or earlier.
4. Non-Melanoma Skin Cancer (NMSC) pathological diagnosis of confirmed squamous cell carcinoma (SCC) or basal cell carcinoma (BCC).

5. Histopathological Grade: G1 (well differentiated); G2 (moderately differentiated) or Gx (not assessed).
6. One lesion is treated, or more than one lesion is treated with a minimum of a 5 mm gap between the edges of the lesion margins.
7. Required retrospective data is existing and sufficient.

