#### Data/Specimen Collection Procedures and Frequency

- Study data will be retrospectively collected from already existing documentation in patient files at the participating sites.
- Study staff will perform an initial review of the existing patient charts for patients who were treated with SRT-100™ for NMSC prior to January 1, 2015. The selected charts will be further reviewed for satisfaction of inclusion criteria and presence of required data elements. The study staff will extract the required information from the patient charts and enter it into an Excel database provided by the study Sponsor.
- The data elements of patient demographics, lesion diagnostic variables and characteristics, lesion size and margins, treatment duration, treatment dosage and schedule, treatment outcomes (particularly cured vs, non-cured) and follow-up outcome variables (particularly incidence of lesion recurrence) will be recorded.
- Data collection will be ongoing until no additional qualifying patient charts are identified at the respective study sites.

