### **6.2. DATA COLLECTION**

Study staff at each of the study test sites will perform an initial review of the existing patient charts for those who received a diagnosis of NMSC for which they received SRT-100™ treatment prior to January 1, 2015 and for which post-procedure follow-up data is available. From this initial review, selected charts will be further reviewed for the satisfaction of inclusion criteria and presence of required data elements. The study staff will extract the required data elements from the patient charts and enter them directly into the Excel database provided by the study Sponsor.

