**F. Follow-Up:**

1. Time in months since the most recent follow-up since end of treatment
2. Recurrence: Yes/No
3. Recurrence treatment and outcome (as applicable)
4. Follow-up notes (as applicable)

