#### **10.1.1. Cure Rate**

Cure rate will be calculated as the percentage of lesions that attained complete cure following treatment completion, reported as the overall success rate.

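### Entry requires follow-up and undefined data sufficiency, so the cure rate omits an uncounted group of treated lesions and may be biased in either direction

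*Combined protocol and SAP*

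**What the plan says.** Two conditions on post-treatment information govern entry.

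- **Follow-up must exist.** Section 5.4 defines the population as treated patients "who have follow-up data and who satisfy each of the study inclusion criteria and none of the exclusion criteria". The same condition appears in the Abstract (Setting/Participants) and in Sections 5.3.2, 6.1, 6.2 and 7.4. It is not one of the seven numbered inclusion criteria.
- **The data must be adequate.** Criterion 7 in Section 5.4.1 reads "Required retrospective data is existing and sufficient". Section 6.2 has site staff apply it: "selected charts will be further reviewed for the satisfaction of inclusion criteria and presence of required data elements". Neither section lists the mandatory items or sets a threshold.

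The items extracted include the outcome. According to the Abstract, "treatment outcomes (particularly cured vs, non-cured) and follow-up outcome variables (particularly incidence of lesion recurrence) will be recorded". Section 6.3 lists cure status under Outcomes and, separately under Follow-Up, "Recurrence: Yes/No". It also lists covariates such as TDF and lead cutout size.

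Section 5.3.1 points another way on completeness: "All applicable and available data elements as specified in this study protocol will be recorded for each patient".

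The primary result is defined in Section 10.1.1: "Cure rate will be calculated as the percentage of lesions that attained complete cure following treatment completion, reported as the overall success rate". The end of Section 3 says that pooling many sites will make the findings representative of the general patient population.

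**The concern.** A lesion's place in the denominator depends on what happened after treatment: whether the patient came back, and whether someone at the site judged the chart complete enough. Under Sections 6.2 and 7, the staff who screen the chart also extract the outcome from it, and no rule keeps the eligibility decision independent of that outcome. If cured and non-cured lesions differ in their chance of having a usable record, the percentage in Section 10.1.1 is biased, and enrolling more sites does not remove the bias.

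The plan would give a reader no means of judging this. Under Section 7.2.1, codes are issued in order of entry to suitable records, so a rejected chart receives no number. There is no planned count of all treated lesions, no log of exclusions with reasons, no rule for a missing outcome and no sensitivity analysis. What is at stake is the headline success rate and the claim that it generalises.

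**Working it through.** The plan gives no target cure rate, sample size or expected exclusion fraction, so it has no figure of its own to reproduce. The calculations below are illustrations, and **every input is an assumption**. The 95% level is only a scale. It comes from the cited earlier study in Section 3, whose 5-year Kaplan-Meier recurrence was 5.0% (100 − 5.0 = 95.0% recurrence-free), which is not the same quantity as cure.

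**1. Bounds on the all-treated rate.** Let c be the cure rate in included lesions, m the fraction of treated lesions excluded, and q the cure rate in excluded lesions. Then

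all-treated rate = c(1 − m) + q·m.

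The worst case sets q = 0 and the best case q = 1, so the interval is m wide whatever the value of c. With c = 0.95:

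| m | worst: 0.95(1 − m) | best: 0.95(1 − m) + m |
|---|---|---|
| 0.10 | 85.5% | 95.5% |
| 0.20 | 76.0% | 96.0% |
| 0.30 | 66.5% | 96.5% |

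An intermediate case with m = 0.20 and q = 0.80 gives 0.76 + 0.16 = 92.0%.

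**2. Bias from unequal inclusion.** Let p be the true cure rate, and s1 and s0 the inclusion probabilities of cured and non-cured lesions. Then

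observed rate = p·s1 / [p·s1 + (1 − p)·s0].

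With p = 0.95:

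| s1 | s0 | calculation | observed | bias (points) |
|---|---|---|---|---|
| 0.8 | 0.8 | 0.76/0.80 | 95.0% | 0 |
| 0.8 | 0.6 | 0.76/0.79 | 96.2% | +1.2 |
| 0.8 | 0.4 | 0.76/0.78 | 97.4% | +2.4 |
| 0.6 | 0.8 | 0.57/0.61 | 93.4% | −1.6 |
| 0.4 | 0.8 | 0.38/0.42 | 90.5% | −4.5 |

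**3. Comparison with sampling error.** The 95% half-width is 1.96·√(0.95 × 0.05/n), treating lesions as independent. It is 1.9 points at n = 500 and 1.0 point at n = 1715, the size of the cited study. All four non-zero biases exceed the half-width at 1715, and two of them (+2.4 and −4.5) exceed it at 500.

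**4. Which missing items exclude a lesion.** Criterion 7 and Section 6.2 make the presence of required items a condition of entry. Section 5.3.1 has the available items recorded. Section 6.3 marks no item as mandatory. A chart that lacks TDF or cutout size is therefore eligible on one reading and ineligible on the other, and each site must choose.

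**The case against.** The strongest reply is that the entry rules select on whether data exist, never on what they show. This stands. A reader might infer that the cure rate is calculated on lesions chosen by outcome, or that it must be too high. The documents support neither reading: equal inclusion gives no bias, and unequal inclusion can push the rate either way, for instance if failures are treated elsewhere or if cured patients do not return.

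A reader might also infer that a lesion lacking TDF or cutout size is removed from every analysis, Kaplan-Meier included. That is one reading of criterion 7, but Section 5.3.1 suggests that gaps may be tolerated. Only the ambiguity is established.

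Nor are excluded lesions lost for good. Section 7.2 keeps source records at the sites, and the link destroyed under Section 7.2.1 concerns entered records, so rescreening could recover a count. The gap is that no count is planned.

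Two further defences have less force. Lesions without follow-up add nothing to the Kaplan-Meier estimate, which is true, but the percentage in Section 10.1.1 still loses them. A chart review can use only what is recorded, which is also true, but records of diagnosis and treatment are enough to identify the cohort. Requiring outcome information for entry is a separate and avoidable choice.

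**Conclusion.** The point holds as a risk of selection bias that the plan neither measures nor bounds. Eligibility depends on follow-up and on undefined sufficiency, the primary percentage omits treated lesions without usable records, and nothing in the plan supports the representativeness stated in Section 3 for the lesions left out.

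The direction and size of any bias cannot be determined from the documents. On the assumed inputs, 20% exclusion with 95% cure among included lesions leaves the all-treated rate anywhere between 76.0% and 96.0%. The lower end requires every excluded lesion to be a failure and the upper end requires every one to be cured, so these are limits and not estimates. The unequal-inclusion cases shown give biases from −4.5 to +2.4 points, and equal inclusion gives none. The change should be made because the plan as written cannot show which case applies.

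**What to change.** - **Entry.** Remove the follow-up condition from the Abstract (Setting/Participants) and from Sections 5.3.2, 5.4, 6.1, 6.2 and 7.4. Amending criterion 7 alone would leave lesions without follow-up ineligible. Replace criterion 7 with a minimum record of diagnosis and SRT-100 treatment that does not depend on outcome, and align the chart-screening wording in the Abstract and in Sections 6.2 and 7.4. Enter every treated lesion that meets criteria 1 to 6.
- **Outcome coding.** Keep any cure status recorded at treatment completion, because Section 6.3 holds it separately from follow-up. Code cure as unknown only where none is recorded, and set follow-up time to 0 if there is no later visit.
- **Missing covariates.** State that lesions lacking items such as TDF or cutout size stay in the cure-rate and Kaplan-Meier analyses.
- **Reporting in Section 10.1.1.** Give the cure rate on assessed lesions, with two bounds on all treated lesions: unknown counted as not cured, and unknown counted as cured. Compare assessed with unassessed lesions on baseline variables.

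The cost is small. Sites already screen these charts, so the extra work is a short row for each additional lesion, drawn from existing records as Section 6.1 requires. The lower bound will look less favourable than the single percentage now planned.

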#### **5.4.2. Exclusion Criteria**

1. Lesions of etiology other than non-melanoma skin cancer (NMSC).

## **6. STUDY PROCEDURES**

### **6.1. RESEARCH DATA SOURCE**

The research data source in this study is existing recorded information in patient files at the study test sites from patients who received SRT-100™ treatment for NMSC prior to January 1, 2015 and for whom follow-up data is available. This study is a pure retrospective analysis. No additional information will be collected for any subject in this study other than the required information that is already existing in their patient file.

### **6.2. DATA COLLECTION**

Study staff at each of the study test sites will perform an initial review of the existing patient charts for those who received a diagnosis of NMSC for which they received SRT-100™ treatment prior to January 1, 2015 and for which post-procedure follow-up data is available. From this initial review, selected charts will be further reviewed for the satisfaction of inclusion criteria and presence of required data elements. The study staff will extract the required data elements from the patient charts and enter them directly into the Excel database provided by the study Sponsor.

### **6.3. DATA ELEMENTS**

The following demographic, lesion, diagnostic, treatment and outcome variables will be recorded from the suitably identified existing patient medical records.

#### **A. Patient Information and Demographics:**

1. Gender
2. Age at treatment start

3. Ethnicity
4. Significant comorbidities

B. Lesion Diagnostic Variables and Characteristics:

1. Pathology diagnosis
2. Diagnosis subtype/variant
3. Other pathology
4. Recurrent lesion (yes/no)
5. Previous treatment if recurrent
6. Lesion location (no restrictions): scalp, mastoid, forehead, cheek, nose, ear, chin, lips, neck, upper arm, lower arm, hand, upper leg, lower leg, foot.

C. Lesion Size and Margins:

1. Lesion size
2. Treatment margin
3. Lead cutout size
4. Applicator size

D. Treatment Dosage and Schedule:

1. Treatment dose
2. Number of treatments
3. Number of treatments per week
4. Treatment span(days)

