### **1.6. CONFIRMATORY DIAGNOSIS OF NMSC**

Dermoscopy is commonly used as an initial aid for early evaluation, identification and diagnosis of NMSC. Confirmatory diagnosis is subsequently made through clinical (physical) examination followed by histological excision (biopsy – most commonly punch or shave biopsy).

- (i) Clinical assessment of the lesion involves evaluation of tumor size (diameter) and anatomical location; determination of lesion recurrence; determination of lesion connection to underlying structures such as muscle, cartilage or bone; classification/grading of the borders (SCCs); and notation of evidence of prior surgery or treatment. If an SCC is suspected, lymph nodes are examined for potential metastasis.
- (ii) Histological examination of NMSC is critical to confirming the clinical assessment, confirming the histopathological type as BCC or SCC, and if applicable, the degree of differentiation of SCC. Histopathological assessment involves evaluation of tumor depth; presence of ulceration (BCCs); morphological subtype; histopathological features (SCCs); and perineural or vascular involvement.

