## 2 STUDY JUSTIFICATION AND RATIONALE

Non-melanoma skin cancers are the most common form of cancers with the incidence increasing at a rapid rate. Current guidelines (e.g. National Comprehensive Cancer Network (NCCN) and American Academy of Dermatology (AAD)) suggest that surgical treatments remain the most effective option for the management of most cases of BCC and SCC.

Clinical recommendations for radiation therapy (RT) are typically based on consideration of RT as a single category without differentiating between the different applications of the different available modalities. As different radiotherapy modalities and dosing have been shown to result in widely varying outcomes, with recurrence rates ranging from 2.8% to 30%, such generalized recommendations can be misleading. AAD guidelines group newer technologies such as high-dose electronic brachytherapy (EBT) and SRT as new therapies. Though the AAD has since clarified these modalities in an addendum position statement it continues to refer to SRT as a “new” technology that “differs substantially from traditional external beam radiation therapy” and one in need of “research on long term outcomes.”

This retrospective study has been designed to focus on efficacy and safety of superficial radiation therapy (SRT) for NMSC and to specifically address this AAD-highlighted deficiency and need for long-term evaluation of ‘new’ technologies for the treatment of NMSC. Evaluation of SRT for NMSC in this study will be via review of retrospective data for procedures delivered by the Sensus Healthcare SRT-100™. Sensus Healthcare’s SRT-100™ has been cleared by the U.S. Food and Drug Administration (U.S. FDA) for the treatment of non-melanoma skin cancer and keloids.

The SRT-100™ delivers a precise, calibrated dose of superficial radiation therapy that only penetrates skin deep, resulting in a virtually painless treatment can be safely administered in the physician’s office.

Low-dose SRT effectively destroys BCC and SCC without any invasive cutting, bleeding or stitching. There is no need for anesthesia, no risk of infection or scarring and no need for reconstructive plastic surgery. Healing time is quick with minimal to no post-treatment downtime or lifestyle restrictions. It is therefore both a viable and highly desirable alternative to invasive, painful and higher-risk surgical procedures.

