5. TDF
6. TX energy KV: 50, 70, 100
7. Total dose
8. Break duration (days or N/A)

E. Outcomes:

1. Cured: Yes/No
2. Adverse Events: yes, no
3. Adverse Events description (as applicable)
4. Notes (as applicable)

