#### **10.1.2. Recurrences and Complications**

Each identified incidence of lesion recurrence, complication or adverse event recorded at any point throughout the treatment and follow-up evaluation phase will be explored descriptively. Statistical evaluation of recurrences will be as follows:

- (i) *Kaplan-Meier Survival Probability Estimates* will be calculated across the duration of available follow-up data, reporting survival probability estimates, and lower and upper limits of the 95% Confidence Interval by follow-up year.
- (ii) *Log-Rank Test* will be performed to evaluate for differences in recurrence-free survival between lesion types.
- (iii) *Multivariate Cox Regression Analysis* will be performed to account for the contribution of the potential influential factors of gender, age, lesion type, lesion size, total treatment dosage and TDF to recurrence-free survival.

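### Tumour depth is not a named data element, and subtype, its recorded partial proxy, is not in the Cox model, so the dose and TDF hazard ratios are open to confounding by depth of unknown size

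*Combined protocol and SAP*

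**What the plan says.** Section 1.6 describes the pathology work-up: "Histopathological assessment involves evaluation of tumor depth; presence of ulceration (BCCs); morphological subtype; histopathological features (SCCs); and perineural or vascular involvement". Section 2 says the device "delivers a precise, calibrated dose of superficial radiation therapy that only penetrates skin deep".

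Section 6.3 sets out the data to extract. Under "B. Lesion Diagnostic Variables and Characteristics" it asks for diagnosis, "2. Diagnosis subtype/variant", "3. Other pathology", recurrent status, previous treatment and location. Part C adds lesion size, which section 10.2.2(iii) treats as a diameter in centimetres. Part D records dose, TDF and beam energy ("6. TX energy KV: 50, 70, 100"). Neither depth nor perineural or vascular involvement is named. Section 7 tells staff to extract only the required elements. Section 7.2.1 has the sheets linking codes to charts destroyed once the data are checked.

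The Cox model in section 10.1.2(iii) takes gender, age, lesion type, "lesion size, total treatment dosage and TDF to recurrence-free survival". Lesion type means BCC or SCC (section 10.2.2(i)). Subtype and beam energy are not covariates. The relationship between outcomes and dosage or fractionation is a secondary objective (Abstract; section 5.1.2).

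**The concern.** If treatment reaches only skin deep, tumour depth bears on whether it reaches the whole tumour, and so plausibly on recurrence. Dose was not randomised in these charts. If clinicians also varied dose or TDF with depth, the Cox coefficients for dose and TDF would mix the effect of dose with the reason it was given.

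Eligibility does not close this gap. Section 5.4.1 restricts histological grade and admits lesions whose grade was not assessed. Section 5.4.2 excludes only lesions that are not NMSC. Section 1.8 speaks of primary, non-aggressive tumours, but no criterion enforces that.

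At stake is the interpretation of one secondary objective. Section 10.2.4 only compares dose variables between BCC and SCC, so the Cox model carries the whole dose-recurrence question. Once the link sheets are gone, depth cannot be matched back to the coded records.

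**Working it through.** The plan gives no sample size, power or target effect, so there is no figure to reproduce. The check has four steps.

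**1. How well do the planned covariates stand in for depth?** In the single-practice study summarised in section 3:
- superficial BCC: 81/712 = 11.4%
- SCC in situ: 861/994 = 86.6%
- both together: (81 + 861)/1715 = 54.9%

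If this registry has a similar mix, BCC versus SCC is a poor substitute for depth, because SCC would be mostly in situ and BCC mostly not superficial. Subtype carries more of the information, and it is the variable left out of the model.

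**2. Size of the possible bias.** For an omitted binary confounder and a rare event, the dose hazard ratio (HR) is multiplied by about

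B = [1 + p1(g − 1)] / [1 + p0(g − 1)],

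where g is the recurrence HR for deep versus shallow lesions, and p1 and p0 are the shares of deep lesions at higher and lower dose. All three are assumptions. With a true dose HR of 1.0, the HR that would be seen is:

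| p1 / p0 | g = 1.5 | g = 2 | g = 3 |
|---|---|---|---|
| 0.45 / 0.45 | 1.00 | 1.00 | 1.00 |
| 0.5 / 0.4 | 1.04 | 1.07 | 1.11 |
| 0.6 / 0.3 | 1.13 | 1.23 | 1.38 |
| 0.7 / 0.2 | 1.23 | 1.42 | 1.71 |

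For example, the last cell is (1 + 0.7×2)/(1 + 0.2×2) = 2.4/1.4 = 1.71. If deeper lesions received less dose, the factor inverts: 1.4/2.4 = 0.58.

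**3. A protective dose effect.** Assume a true dose HR of 0.70, 25% of lesions deep, and higher dose given to 60% of deep and 20% of shallow lesions. Then p1 = 0.15/0.30 = 0.50 and p0 = 0.10/0.70 = 0.143. For g = 1.5, 2, 3 and 4, B is 1.17, 1.31, 1.56 and 1.75, so the HR seen is 0.82, 0.92, 1.09 and about 1.22. It crosses 1 where B = 1/0.70 = 1.43, at g of about 2.45. With a weaker link (40% versus 25%), p1 = 0.10/0.2875 = 0.348 and p0 = 0.15/0.7125 = 0.211. The HR seen is then 0.78 at g = 2 and 0.84 at g = 3, and would cross 1 only at g of about 10.

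**4. Would recorded variables remove it?** Simulated Cox fits (n = 200,000, true dose HR 1.0, five-year recurrence about 4.5% to 7%) agreed with the formula:
- g = 3, 0.7/0.2: 1.72 without depth, 1.46 with a proxy that classifies depth correctly 80% of the time, 1.01 with depth itself.
- g = 2, 0.6/0.3: 1.22, 1.14 and 0.99.

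Diameter did less. In the step 3 setting at g = 3, with diameter and depth correlated at 0.3 (assumed), two simulated set-ups gave a diameter-adjusted HR of 1.09 and 1.04. Adding depth brought these to 0.69 and 0.67, close to the true 0.70. The second set-up also let diameter raise recurrence (log HR 0.2 per SD).

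**The case against.** The strongest reply is that confounding is possible but not shown. It requires depth to be associated with dose or TDF after the other covariates, and no section says how dose, TDF or beam energy was chosen. With no association the bias is nil, and with a weak one (0.5/0.4) it is 4% to 11%. This stands. A reader might infer that the dose model is confounded by depth as a matter of fact; the documents do not support that. Nor do they support saying that the dose effect will reverse, which needs both the strong assumed link and a depth HR above about 2.45.

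A second reply is that depth is partly captured. Subtype is recorded, beam energy may reflect intended depth, and the undefined pathology field could hold invasion findings. So it would be wrong to say that nothing on depth or invasion is collected. But subtype and beam energy are outside the Cox model, an undefined field will be filled unevenly, and an imperfect proxy reduces the bias without removing it.

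Third, precision may swamp the bias. At the earlier study's size, 5.0% recurrence gives at most about 1715 × 0.05 = 86 events. With 30% at higher dose, the SE of the log HR is about 1/√(86×0.3×0.7) = 0.24, so the 95% interval spans a factor of about 1.6 each way, wider than most of the biases above. This stands too, and it limits how many terms can be added. It does not make the bias harmless, because a larger registry shrinks the interval but not the bias.

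Finally, section 1.6 is general background and does not show that these charts report depth. The skin-deep argument also does not extend to perineural or vascular involvement, for which the documents give no link to dose. Both points stand.

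**Conclusion.** The point holds as a gap in data capture and adjustment, not as a demonstrated bias. Depth is not a named element, its best recorded proxy is left out of the only dose-recurrence model, and confounding of the dose and TDF hazard ratios by depth therefore cannot be ruled out. Under the assumed inputs the distortion runs from none to a factor of about 1.7, in either direction. Those inputs (g, p1, p0) come from nowhere in the documents, so the range is illustrative.

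A reader might extend this to the headline results. The documents do not support that: the cure rate (section 10.1.1) and the overall Kaplan-Meier estimates use no covariate adjustment for dose. The objectives speak of relationships and potential differences, so no causal dose claim is planned. This is an inexpensive improvement to a secondary analysis, worth making while the charts are open.

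**What to change.** **Section 6.3 B.** Add tumour depth as reported (mm or level, or not reported). As a second priority, add perineural or vascular involvement (yes, no, not reported). State that both fields are non-mandatory, so that inclusion criterion 7 and the chart screen in section 6.2 do not drop lesions lacking them. Complete the extraction before the link sheets in section 7.2.1 are destroyed.

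**Section 10.1.2(iii).** Keep the planned model. Add a sensitivity fit with subtype group (in situ or superficial versus other) and, where reported, depth category, with the number of terms limited by the number of recurrences. Report the dose hazard ratio with and without these terms, and label the result an association. The subtype term uses data already collected, so it remains possible even if depth is rarely reported.

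**Cost.** Two fields from a pathology report already being read, and a few lines of analysis plan. Depth will be missing from some reports, so adjustment will be partial. The extra terms cost precision: with about 86 recurrences, going from 6 parameters to 9 (one for subtype, two for a three-level depth variable) takes events per parameter from about 14 to about 9.5.
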